3.1.1 Screening/Run-in Period (Up to 4 weeks)

The purpose of the Screening/Run-in Period is to ensure that all enrolled subjects are on stable doses of baseline medications, do not have “white coat” hypertension, can demonstrate proper and reliable use of the BP monitoring device prior to study drug treatment, and meet all study inclusion/exclusion criteria.

The Screening/Run-in Period will consist of four Screening Visits (S1, S2, S3, and S4) that are approximately 7 days (at least 4 days but no more than 10 days) after the prior screening Visit (Appendix A).

Visit S1: Each subject will be issued a HBP monitor and provided with training on device use. Subjects will be instructed to measure HBP in triplicate twice daily after Visit S1 (Section 7.3.2.1).

Visits S2, S3 and S4: Two types of office BP measurements will be performed before other scheduled activities (except for S4 where the EQ-5D-5L will be the first assessment). Both measurements will be performed with the subject alone after 5 minutes of seated rest (Section 7.3.2.2):

1. Performed by an automatic oscillometric BP monitoring device that can measure BP in triplicate (automated Office BP, AOBP)
2. Performed by the subject using their issued HBP monitoring device in triplicate (subject-measured BP, SMBP)

Note: Study staff should not be present while both office BP measurements are being performed. Subjects will be instructed to bring their issued HBP device to every visit.

To be eligible for this study, subjects will be required to meet all of the following criteria (see Section 4 for complete criteria):

1. AOBP SBP 135 to 160 mmHg at each Screening Visit; however, AOBP SBP may be < 135 mmHg at either S2 or S3 Visits
2. eGFR of $25 - \leq 45$ mL/min/1.73 m² (mean [calculated by the Interactive Web Response System – IWRS] of two values measured at S1 and S3 (or 7 to 28 days apart) during the Screening/Run-in Period)
3. Local laboratory measurements of K⁺ level of 4.3 – 5.1 mEq/L obtained at Visits S1, S3 and S4 (all measurements must be within range)
4. Does not meet any exclusion criteria

If hemolysis of the local sample is detected or suspected (see Section 7.1.1) at Screening Visits (S1 and S3), a repeat of the potassium measurement from a separate blood draw will be performed within 1 day. If the repeated potassium level does not meet entry criteria, then the subject is considered a Screen Failure.

For Visit S4, if hemolysis of the local sample is detected or suspected, the subject is not randomized and a repeat of the potassium measurement from a separate blood draw will be

performed within 1 day. If the subject qualifies, the subject will be randomized on the same day. All assessments performed at Visit S4, aside from the hemolyzed potassium level, will be considered baseline assessments, and the day the repeat potassium measurement was obtained will be designated the Randomization/Baseline (Day 0) Visit. If the repeated potassium level does not meet entry criteria, then the subject is considered a Screen Failure.

If a subject fails any qualifying criteria, at any of the Screening Visits, the subject will be considered a Screen Failure at that Visit. Subjects who meet all study entry criteria except for eGFR and/or serum potassium will be screen failures but may be rescreened once at least 2 weeks after initial screen failure (Section 6.1.5).

3.1.2 Double-Blind Treatment Period (12 weeks)

Randomization (Baseline – Day 0) Visit:

Subjects who meet all eligibility criteria at Visit S4 will be randomized on the same day to either patiromer or placebo treatment (1:1) with stratification based on the local potassium level at Visit S4 ($4.3 - < 4.7$ or $4.7 - 5.1$ mEq/L) and history of Type 1 or 2 diabetes mellitus (Yes or No). The S4 assessments will become the baseline assessments. A combined visit (S4/Randomization [Baseline/Day 0]) will be recorded for all randomized subjects.

All randomized subjects will be provided with detailed instructions for when to take spironolactone, patiromer/placebo, and other baseline medications after considering the subject's current medication regimen, patiromer/placebo instructions regarding administration, and subject preference (see Section 5.5.1). The subject will be instructed to begin taking study drugs (spironolactone and patiromer/placebo) on the following day (Day 1) and on the morning of their subsequent study visits to delay taking their blood pressure medications until office blood pressure measurements have been completed.

Treatment Period Visits (refer to Appendix A):

During the Double-Blind Treatment Period, study visits will occur at Week 1 (Day 8 ± 3 days), Week 2 (Day 15 ± 3 days), Week 3 (Day 22 ± 3 days), Week 4 (Day 29 ± 3 days), Week 6 (Day 43 ± 7 days), Week 8 (Day 57 ± 7 days), Week 10 (Day 71 ± 7 days), and Week 12 (Day 85 ± 7 days).

Patiromer/placebo treatment:

Patiromer/placebo will be taken at a starting dose of two packets once daily (QD). Based upon the treatment algorithm, patiromer/placebo will be increased in two-packet per day increments for local $K^+ > 5.1$ mEq/L in intervals of at least 1 week up to a maximum dose of six packets QD. For subjects with $K^+ < 4.0$ mEq/L, patiromer/placebo dose will be decreased by at least two packets per day. The minimum dose of patiromer/placebo is 0 packets. Patiromer/placebo should be taken with food, at least 3 hours before or 3 hours after administration of other concomitant medications including spironolactone. Refer to Appendix B for complete dosing and monitoring instructions.

Throughout the Double-Blind Treatment Period, subjects who develop $K^+ \geq 5.5$ mEq/L that cannot be managed with blinded patiromer/placebo escalation according to the treatment algorithm (refer to Appendix B) will discontinue spironolactone and patiromer/placebo, but will remain in the study (refer to Appendix C) and complete all remaining scheduled visits. After discontinuation of spironolactone and patiromer/placebo, hyperkalemia may be treated using the standard of care per the Investigator's judgment.

Spironolactone treatment:

Spironolactone will be initiated for all randomized subjects on Day 1, at a dose of 25 mg taken orally QD. At Week 3, for subjects with AOBP SBP ≥ 120 mmHg and $K^+ \leq 5.1$ mEq/L, spironolactone will be increased to 50 mg QD. For subjects with $K^+ > 5.1$ mEq/L, 25 mg daily dose of spironolactone will be continued until the first subsequent visit when K^+ is ≤ 5.1 mEq/L (and AOBP SBP ≥ 120 mmHg), at which time spironolactone will be increased to 50 mg QD.

Subjects with AOBP SBP < 120 mmHg at the Week 3 Visit will continue their 25 mg daily dose, unless symptoms of hypotension are present with SBP < 120 mmHg, or if SBP is < 100 mmHg (Appendix C), in which case the spironolactone dose may be reduced to 25 mg every other day or discontinued altogether, at the discretion of the Investigator. Spironolactone may be reduced or discontinued for SBP < 100 mmHg. If spironolactone is discontinued, patiromer/placebo must be discontinued at the same time. These subjects will remain in the study and be followed per protocol.

Note: During all study visits, if a subject experiences symptoms of hypotension with AOBP SBP < 120 mmHg, or if SBP < 100 mmHg, spironolactone dose may be reduced (e.g., 25 mg every other day) or discontinued at the discretion of the Investigator.

Throughout the treatment period, creatinine will be measured at each study visit (and may be measured at Unscheduled Visits). Subjects should be monitored for changes in renal function, especially during periods of medication changes or adjustments. Acute reductions in GFR have been seen with the initiation of spironolactone, similar to those seen with initiation of ACE inhibitors and ARBs that have been attributed to transient changes in glomerular hemodynamics (Bianchi, 2015, KDIGO, 2012). These changes typically do not impact long-term renal function. In this study, use of the KDOQI recommendations for the detection and management of early decrease in GFR (when initiating ACE inhibitors/ARBs) for monitoring the initiation of spironolactone (NKF, 2004) should be considered.

Based on KDOQI guidelines:

- An early decline in eGFR is defined as $> 15\%$ reduction from baseline within 4 weeks of initiation of spironolactone
- For decreases in eGFR up to 30%, no changes to spironolactone dosing need to be made, and eGFR may be followed routinely
- Decreases in eGFR $> 30\%$, however, should prompt a search for other etiologies of abrupt renal function decline, including prerenal and postrenal causes, toxic reactions, and renal artery disease

- For a decline in eGFR from 30 to 50%, the spironolactone dose should be decreased and the eGFR followed weekly. If the eGFR does not return to within 30% of baseline within 4 weeks, spironolactone should be discontinued
- Spironolactone should be discontinued for a decline in eGFR > 50% and eGFR should be followed at least weekly until eGFR has returned to within 15% of the baseline value, and biweekly thereafter through the end of the study

Blood pressure management should proceed as outlined below.

Blood pressure management:

When spironolactone has been discontinued and AOBP SBP is ≥ 165 to < 200 mmHg, alternative antihypertensive medication may be added to the blood pressure regimen (Appendix D). Baseline medication doses should not be changed except for AE-related reasons where changes to baseline medications can be justified by the Investigator (e.g., increases in loop diuretics for new edematous states or discontinuation of baseline medication for drug-related AEs).

For subjects on spironolactone 25 mg QD (before Week 3), spironolactone may be increased to 50 mg QD before the Week 3 Visit for persistent SBP ≥ 180 mmHg (assessed by AOBP), at the investigator's discretion. For subjects on spironolactone 50 mg QD, additional BP medication may be added to control persistent SBP ≥ 165 mmHg (assessed by AOBP) at the discretion of the investigator. This decision may reflect the degree of blood pressure elevation, the time since last spironolactone dose adjustment, and the level of urgency to lower blood pressure, in the investigator's judgment. Baseline medication doses should not be changed except for AE-related reasons where changes to baseline medications can be justified by the Investigator (e.g., increases in loop diuretics for new edematous states or discontinuation of baseline medication for drug-related AEs).

For all subjects (on or off spironolactone) with AOBP ≥ 200 mmHg, subjects should be treated in accordance with the standard of care for BP management and the Investigator's judgment (i.e., additional medications or change in baseline medication dose are permitted, Appendix D).

Note: All subjects will remain in the study and complete all study assessments in accordance with the protocol.

Unscheduled Visits:

For subjects with study drug (spironolactone or patiromer/placebo) modifications based on BP assessments or potassium levels, an Unscheduled Visit should be conducted within 1 week after this modification unless the next scheduled visit is within 1 week of the study drug modification, in which case the subject will return at the next scheduled visit.

Upon completion of all Double-Blind Treatment Period assessments at the Week 12 Visit (or ET Visit), subjects will discontinue all study drugs that they are receiving (patiromer/placebo/spironolactone). After study drug discontinuation, the treatment of hypertension should proceed in accordance with the standard of care for BP management and the Investigator's judgment.

3.1.3 Follow-up Visit (2 Weeks after Week 12 or ET Visit + up to 7 day window)

All subjects will return for a Follow-up Visit, 2 weeks after the Week 12 Visit (+ up to 7 days, if necessary). The Investigator may request the subject to return to the study site prior to the 2-week Follow-up Visit to evaluate potassium levels, AOBP, or AEs, at his/her discretion. In the case where a subject completes the Follow-up Visit prior to 2 Weeks, the subject will receive a Follow-up Phone Call at 2 weeks (+ up to 7 days) after Week 12 or ET Visit.

Subjects who terminate early from the study will complete the ET Visit assessments and return for a Follow-up Visit 2 weeks (+ up to 7 days) after the ET Visit.

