--	--

	
diabetes mellitus (Yes or No). The S4 assessments will become the baseline assessments. A combined visit (S4/Randomization [Baseline/Day 0]) will be recorded for all randomized subjects.
 
All randomized subjects will be provided with detailed instructions regarding when to take spironolactone, patiromer/placebo, and other baseline medications after considering the subject's current medication regimen, patiromer/placebo instructions regarding administration, and subject preference (see Section 5.5.1). The subject will be instructed to begin taking study drugs (spironolactone and patiromer/placebo) on the day following randomization (Day 1) and on the morning of their subsequent study visits to delay taking their blood pressure medications until office blood pressure measurements have been completed.
 
Treatment Period Visits (refer to Appendix A):
 
During the Double-Blind Treatment Period, study visits will occur at Week 1 (Day 8 ± 3 days), Week 2 (Day 15 ± 3 days), Week 3 (Day 22 ± 3 days), Week 4 (Day 29 ± 3 days), Week 6 (Day 43 ± 7 days), Week 8 (Day 57 ± 7 days), Week 10 (Day 71 ± 7 days), and Week 12 (Day 85 ± 7 days).
 
Patiromer/placebo treatment:
 
Patiromer/placebo will be taken at a starting dose of two packets once daily (QD). Based upon the treatment algorithm, patiromer/placebo will be increased in two-packet per day increments for local $K^+ > 5.1$ mEq/L in intervals of at least 1 week up to a maximum dose of six packets QD. For subjects with $K^+ < 4.0$ mEq/L, patiromer/placebo dose will be decreased by at least two packets per day. The minimum dose of patiromer/placebo is 0 packets. Patiromer/placebo should be taken with food, at least 3 hours before or 3 hours after administration of other oral concomitant medications including spironolactone. Refer to Appendix B (Patiromer/Placebo Titration) for complete dosing and monitoring instructions.
 
Throughout the Double-Blind Treatment Period, subjects who develop $K^+ \geq 5.5$ mEq/L that cannot be managed with blinded patiromer/placebo escalation according to the treatment algorithm (refer to Appendix B) will discontinue spironolactone and patiromer/placebo, but will remain in the study (refer to Appendix C, Spironolactone Dosing) and complete all remaining scheduled visits. After discontinuation of spironolactone and patiromer/placebo, hyperkalemia may be treated using the standard of care per the Investigator's judgment.
 
Spironolactone treatment:
 
Spironolactone will be initiated for all randomized subjects on Day 1, at a dose of 25 mg taken orally QD. At Week 3, for subjects with AOBP SBP ≥ 120 mmHg and $K^+ \leq 5.1$ mEq/L, spironolactone will be increased to 50 mg QD. For subjects with AOBP SBP ≥ 120 mmHg and $K^+ > 5.1$ mEq/L at Week 3, the 25 mg daily dose of spironolactone will be continued until the first subsequent visit when K^+ is ≤ 5.1 mEq/L (and AOBP SBP is ≥ 120 mmHg) at which time spironolactone will be increased to 50 mg QD.
 
Subjects with AOBP SBP < 120 mmHg at the Week 3 Visit will continue spironolactone at 25 mg per day.
 
If a subject has an AOBP SBP < 100 mmHg or experiences symptoms of hypotension with AOBP SBP < 120 mmHg, the spironolactone dose may be reduced (e.g., 25 mg every other day) or discontinued at the discretion of the Investigator (Appendix C, Spironolactone Dosing). If spironolactone is discontinued, patiromer/placebo must be discontinued at the same time. These subjects will remain in the study and be followed per protocol.
 
Blood pressure management:
 
When spironolactone has been discontinued and AOBP SBP is ≥ 165 to < 200 mmHg, alternative antihypertensive medication may be added to the blood pressure regimen (Appendix D, Blood Pressure Management and Alternative BP Medication

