Data Safety Monitoring Committee:	A Data and Safety Monitoring Committee (DSMC) will review laboratory and blood pressure data, all reports of AEs (including deaths from any cause), discontinuations from spironolactone and patiromer/placebo, withdrawals from the study, and other data as described in the DSMC Charter. The DSMC Charter will include a description of the scope of planned reviews. When reviewing data, including individual data, the DSMC may be unblinded to treatment assignment (patiromer or placebo).
Study Duration:	Up to 18 weeks: Screening/Run-in Period (up to 4 weeks), Double-Blind Treatment Period (12 weeks), and a Follow-up Visit 2 weeks after the Week 12 Visit.
Study Sites:	Approximately 60 sites.
Study Population:	Approximately 290 subjects will be randomized.
Study Treatments	
Dose and Route of Administration:	
Investigational Products:
 
Patiromer for Oral Suspension: Patiromer will be provided blinded as a powder for oral suspension in packets of 4.2 g each. In the Double-Blind Treatment Period, the starting dose of patiromer will be 8.4 g (two packets, 4.2 g each) QD, taken orally with food.

	
Patiromer QD doses for the study will be adjusted as needed (Appendix B) and will be 0 packets (minimum dose), two packets, four packets, or six packets (maximum dose).
 
Placebo: Placebo (microcrystalline cellulose) will be provided blinded as a powder for oral suspension in packets identical in appearance to patiromer packets. In the Double Blind Treatment Period, the starting dose will be two packets QD, taken orally with food. The number of packets for titration and instructions for use will be the same as for patiromer (Appendix B).
 
Spironolactone: Spironolactone will be administered orally to all subjects at a starting dose of 25 mg QD (at least 3 hours before or after patiromer/placebo) and increased to 50 mg QD at Week 3 (or after) for all subjects with AOBP SBP \geq 120 mmHg and $K^+ \leq$ 5.1 mEq/L (Appendix C).

Eligibility Criteria	

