5.3.3 Dosing and Administration of Patiromer/Placebo and Spironolactone

The starting dose of patiromer/placebo will be two packets QD taken with food for randomized subjects. Patiromer/placebo should be taken at least 3 hours before or 3 hours after administration of other orally administered medications, including spironolactone (see Section 5.5.1 and Investigator's Brochure for additional information).

Based upon the patiromer/placebo treatment algorithm (Section 3.1.2 and Appendix B), patiromer/placebo will be increased in two-packet per day increments for serum $K^+ > 5.1$ mEq/L in intervals of at least 1 week. Doses of patiromer/placebo will be two packets, four packets, and six packets (maximum dose). Patiromer/placebo will be decreased by at least two packets per day for serum $K^+ < 4.0$ mEq/L. The minimum daily dose of patiromer/placebo will be 0 packets.

All subjects will initiate spironolactone 25 mg QD on Day 1. At the Week 3 visit (or after), the spironolactone dose will be increased to 50 mg QD for subjects with AOBP SBP ≥ 120 mmHg and $K^+ \leq 5.1$ mEq/L. For subjects with $K^+ > 5.1$ mEq/L, 25 mg daily dose of spironolactone will be continued until the first subsequent visit when K^+ is ≤ 5.1 mEq/L (and AOBP SBP ≥ 120 mmHg), at which time spironolactone will be increased to 50 mg QD (see Appendix C).

Note: During all study visits, if a subject experiences symptoms of hypotension with SBP < 120 mmHg, or if SBP < 100 mmHg, spironolactone dose may be reduced to 25 mg every other day or discontinued at the discretion of the Investigator.

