^h HBP will be measured by subject twice daily (Section 7.3.2.1) (e.g., at approximately 08:00 hrs and 20:00 hrs) after sitting quietly for at least 5 minutes. The subject will perform triplicate measures, 1 minute apart. HBP training will be performed at the first screening visit and retraining can be performed at any Visit, as needed. HBP monitors are collected from subjects at the Visit Week-12.

ⁱ If hemolysis of the local sample is detected or is suspected (see Section 7.1.1), the sample must be repeated within 1 day for reassessment of potassium.

^j Review potassium results and adjust study medications according to Section 3.1.2 and Appendix B.

^k One of the ACR measurements will be from the 24-hour urine collection (see Section 7.7).

^l Subjects will complete the EQ-5D-5L questionnaire before study staff performs any clinic or study assessments to avoid biasing the subjects' responses.

^m On Day1 patiomer/placebo two packets QD will be taken at home with food and at least 3 hours before or 3 hours after other oral medications including spironolactone. See Appendix B for dosing/titration algorithm.

ⁿ On Day 1 spironolactone (25 mg QD) will be taken at home and increased to 50 mg at Week 3 for subjects with blood pressure ≥ 120 mmHg See Appendix C for dosing instructions.

[figure not shown]

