Appendix C: Spironolactone Dosing

Spironolactone will be initiated for all randomized subjects on Day 1, at a dose of 25 mg taken orally QD. At Week 3, for subjects with AOBP SBP \geq 120 mmHg and K^+ \leq 5.1 mEq/L, spironolactone will be increased to 50 mg QD. For subjects with K^+ $>$ 5.1 mEq/L, 25 mg daily dose of spironolactone will be continued until the first subsequent visit when K^+ is \leq 5.1 mEq/L (and AOBP SBP \geq 120 mmHg), at which time spironolactone will be increased to 50 mg QD.

Subjects with AOBP SBP $<$ 120 mmHg at the Week 3 Visit will continue their 25 mg daily dose, unless symptoms of hypotension are present in which case the spironolactone dose may be reduced to 25 mg every other day or discontinued altogether, at the discretion of the Investigator. Spironolactone may be reduced or discontinued for AOBP SBP $<$ 100 mmHg. If spironolactone is discontinued, patiromer/placebo must be discontinued at the same time. These subjects will remain in the study and be followed per protocol. Note: At any study visit spironolactone dose may be reduced or discontinued for AOBP SBP $<$ 120 mmHg with symptoms of hypotension, or for AOBP SBP $<$ 100 mmHg at the direction of the investigator. Figure 3 describes spironolactone dosing adjustments by Visit and level of SBP (AOBP).

Figure 3: Spironolactone Titration

AOBP = automated office blood pressure; K⁺ = potassium; PI = Investigator; QD = once daily; QOD = once every other day; SBP = systolic blood pressure.

^a If spironolactone is discontinued, patiromer/placebo must be discontinued at the same time. These subjects will remain in the study and be followed per protocol. After study drug discontinuation, the treatment of hypertension should proceed in accordance with the standard of care for BP management and the Investigator’s judgment.

NOTE: At Week 12 all subjects will discontinue all study medications (spironolactone and patiromer/placebo).

Changes in Spironolactone Dosing Based on eGFR

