Throughout the treatment period, creatinine will be measured at each study visit (and may be measured at Unscheduled Visits). Subjects should be monitored for changes in renal function, especially during periods of medication changes or adjustments. Acute reductions in GFR have been seen with the initiation of spironolactone, similar to those seen with initiation of ACE inhibitors and ARBs that have been attributed to transient changes in glomerular hemodynamics (Bianchi, 2015, KDIGO, 2012). These changes typically do not impact long-term renal function. In this study, use of the KDOQI recommendations for the detection and management of early decrease in GFR (when initiating ACE inhibitors/ARBs) for monitoring the initiation of spironolactone (NKF, 2004) should be considered.

Based on KDOQI guidelines:

- An early decline in GFR is defined as > 15% reduction from baseline within 4 weeks of initiation of spironolactone
- For decreases in eGFR up to 30%, no changes to spironolactone dosing need to be made, and eGFR may be followed routinely
- Decreases in eGFR > 30%, however, should prompt a search for other etiologies of abrupt renal function decline, including prerenal and postrenal causes, toxic reactions, and renal artery disease
- For a decline in eGFR from 30 to 50%, the spironolactone dose should be decreased and the eGFR followed weekly. If the eGFR does not return to within 30% of baseline within 4 weeks, spironolactone should be discontinued
- Spironolactone should be discontinued for a decline in eGFR > 50% and eGFR should be followed at least weekly until eGFR has returned to within 15% of the baseline value, and biweekly thereafter through the end of the study

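### The increase to spironolactone 50 mg QD depends only on blood pressure and potassium, while the same sections advise a lower dose after a 30 to 50% eGFR fall, and nothing says which rule governs

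*Protocol*

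**What the plan says.** **The increase.** Protocol 3.1.2 and Appendix C set two conditions at Week 3: AOBP SBP of 120 mmHg or more and K+ of 5.1 mEq/L or less. If both hold, "spironolactone will be increased to 50 mg QD". A subject with K+ above 5.1 stays on 25 mg until the first later visit at which both conditions hold, "at which time spironolactone will be increased to 50 mg QD". Section 5.3.3 says the same ("the spironolactone dose will be increased to 50 mg QD for subjects with AOBP SBP" of 120 mmHg or more, with the potassium condition). The Synopsis dosing row has the dose "increased to 50 mg QD at Week 3 (or after) for all subjects with AOBP SBP" and potassium in range. None of these texts mentions eGFR.

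**The eGFR guidance.** Later in 3.1.2, and in Appendix C under the heading "Changes in Spironolactone Dosing Based on eGFR", sites are asked to consider KDOQI-based recommendations. A fall of up to 30% needs no dose change. For a fall of 30 to 50%, "the spironolactone dose should be decreased and the eGFR followed weekly". If eGFR is not back within 30% of baseline in 4 weeks, or if the fall exceeds 50%, spironolactone should be discontinued.

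**Where sites are sent.** Section 5.2 makes Appendix C the authority for dosing after Day 1, and Appendix C holds both rules. The review step in 6.2.2 has sites look at local potassium and AOBP and then adjust study drugs under 3.1.2 and the appendices. Appendix A notes f and j likewise name AOBP and potassium. eGFR is measured at each scheduled treatment visit, by the central laboratory.

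**The concern.** The titration rule is an instruction; the eGFR guidance is advice. Where both apply to one subject, one raises the dose and the other lowers or stops it. The text gives no exception to the increase and no order of precedence.

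Two things are at stake. The first is safety. Subjects enter with eGFR 25 to 45 mL/min/1.73 m² and potassium of 4.3 to 5.1 mEq/L, and renal events are a named safety outcome. A site that applies the titration rule by its wording raises the dose when the protocol's own renal guidance says to lower it. The second is consistency: two sites can dose similar subjects in opposite directions, each with text to support it.

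Surrounding text adds to the pull toward the increase. In the titration text itself, discretion to reduce the dose is written only for low or symptomatic blood pressure. Section 4.3 describes protocol-specified discontinuations as being for hyperkalemia and hypotension. Section 12.2 allows no deviation without prior written sponsor approval except in a medical emergency, so an investigator who withholds the increase for a falling eGFR could be recorded as deviating.

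**Working it through.** No stated figure of the plan is in question, so the check sets the two rules side by side. In every row AOBP SBP is at least 120 mmHg and K+ is at most 5.1 mEq/L at the visit.

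| Situation | Titration rule | eGFR guidance | Compatible? |
|---|---|---|---|
| Week 3, eGFR down by up to 30% | Raise to 50 mg QD | No change needed on eGFR grounds | Yes |
| Week 3, fall of 30 to 50% known at the visit | Raise to 50 mg QD | Decrease | No |
| Dose reduced before Week 3 for a fall of 30 to 50% seen at Week 1 or 2, eGFR not recovered | Raise to 50 mg QD | Already reduced; stop if not recovered in 4 weeks | No |
| Held at 25 mg at Week 3 for K+ above 5.1, fall of 30 to 50% by the later visit at which K+ qualifies | Raise to 50 mg QD | Decrease | No |
| Fall above 50% known at the visit, still on drug | Raise to 50 mg QD | Stop | No |

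**Timing.** eGFR comes from the central laboratory. I assume that a visit's result is back by the next weekly visit, not on the same day. The value usually in hand at Week 3 is then that of Week 2. A 30 to 50% fall seen at Week 1 or 2 would already have called for a dose below 25 mg QD. So if the guidance was followed, the live conflict at Week 3 is the third row. A direct step from 25 to 50 mg in such a subject needs either a fall that first becomes known around the titration visit or guidance that was not acted on earlier.

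**Size of the dose step.**
- From 25 mg QD: 50 / 25 = 2, a doubling.
- From a reduced dose: the guidance names no reduced dose. If it is 25 mg every other day (the protocol's example for hypotension, assumed here), the daily average is 25 / 2 = 12.5 mg, and 50 / 12.5 = 4, a fourfold step.

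**Renal function at which this happens**, taking the entry limits as baseline values:
- Baseline 25: 25 × 0.70 = 17.5 and 25 × 0.50 = 12.5 mL/min/1.73 m².
- Baseline 45: 45 × 0.70 = 31.5 and 45 × 0.50 = 22.5 mL/min/1.73 m².

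**Search for a tie-breaker.** Section 5.2 points to Appendix C, which contains both rules unranked. Figure 3 is not shown, but its description refers to visit and SBP, and its legend lists K+ and not eGFR. SAP 2.2 names blood pressure and potassium and sends the reader back to the protocol appendices. None of these settles the order.

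**The case against.** The best defence is that the documents read naturally as a general rule followed by a specific safety modification. The Appendix C heading says that the eGFR text concerns changes in spironolactone dosing. The paragraph above the eGFR rules, in both 3.1.2 and Appendix C, asks for renal function to be watched particularly while medication is being adjusted. Following the protocol includes following that guidance, and most nephrologists would.

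Much of this stands. It makes the eGFR-first reading the more likely one for a careful investigator. It does not make it the written rule: the guidance is introduced as something to consider, the increase is not, and the review step omits eGFR.

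A reader might infer that the defect is large because the increase is repeated in many places without an eGFR condition. The repetition does not show that. The Synopsis dosing row, 5.3.3, Appendix A note n ("will be taken at home and increased to 50 mg at Week 3 for subjects with blood pressure" of 120 mmHg or more) and SAP 2.2 are summaries that refer on to Appendix C.

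A reader might also take the Introduction's mean creatinine rise of 1.5 to 1.8 mg/dL under MRAs as evidence of how often falls above 30% will occur. A mean with no standard deviation or time frame does not give that share.

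Finally, one might add that chemistry is optional at unscheduled visits. The guidance already asks for weekly eGFR after such a fall, and 6.5 requires a visit after any study drug modification and permits chemistry there. That item adds little.

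**Conclusion.** The point holds as an unranked conflict between two dosing rules in 3.1.2 and Appendix C. It affects a subject who meets the SBP and potassium conditions and either has an eGFR fall above 30% known at the titration visit or has already been reduced for one. For that subject the instruction as worded is a twofold increase from 25 mg QD, or more from a reduced dose, while the guidance says to decrease or stop.

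The number of such subjects cannot be derived, because the documents give no rate of eGFR decline. The timing argument rests on the assumed turnaround of central results.

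A reader might infer that the primary test is compromised. The documents do not support that. The endpoint, remaining on spironolactone at Week 12, has no dose requirement, so a subject on 25 mg counts the same as one on 50 mg. The eGFR stopping rules do feed the endpoint, so an indirect effect is possible, but neither its size nor its direction can be worked out. The concern is subject safety and consistent dosing, and it should be corrected.

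**What to change.** 1. In 3.1.2 and Appendix C, add a third condition to the increase: *and the latest available central eGFR is not more than 30% below baseline*.
2. In the same two places, state that the eGFR rules take precedence over the increase, and that a subject reduced for eGFR is not raised until eGFR is back within 30% of baseline.
3. Add the latest eGFR to the results reviewed in 6.2.2.
4. Let the Synopsis, Appendix A and SAP summaries refer to Appendix C; they need no eGFR wording of their own.

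The cost is a short amendment. No new test is needed, because central chemistry with eGFR is already drawn at Weeks 1 and 2 and at every later treatment visit. The downside is that slightly fewer subjects reach 50 mg, or reach it later.
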